Section 2 Schedule of Activities	Addition of footnotes 7 and 8 to specify timepoints for activity monitor return, as well as scheduling of optional MRI.	Clarification of timepoints for study site staff, as well as change in how exit interviews are anticipated to be conducted. Exit interviews will now be conducted by expert interviewers from a partner agency rather than trained site staff.
Section 9.1.3 Baseline (day 1) and last dose (day 90) visits	Clarification of language for scheduling of MRI scans	
Section 9.2.4 Patient Reported Outcome Assessments	Addition of language to specify timepoints when CAT, SGRQ, PGRS and PGIC will be measured. Clarification of how exit interview will be conducted (administered by experienced interviewers (by a partner agency) instead of by site staff)	
Section 2 Schedule of Activities	Removal of text: "Any changes in the timing or addition of time points for any planned study assessments must be documented and approved by the relevant study team member and then archived in the sponsor and site study files, but will not constitute a protocol amendment. The IRB/IEC will be informed of any safety issues that require alteration of the safety monitoring scheme or amendment of the ICF."	This text is intended for phase I studies, therefore removed as per latest guidance, since addition of timepoints for assessments in phase II studies will constitute a protocol amendment.

Section # and Name	Description of Change	Brief Rationale
Section 5.5 Dose Justification	
Adjusted drug half-life from 4-7 to 5-8 days.
 
Revision of text so that it now reads:
 
“Results of drug interaction study in healthy volunteers conducted with a prototype strong CYP3A4 inhibitor (itraconazole) showed that exposure to GSK2881078 was only modestly elevated when co-administered with a strong CYP3A4 inhibitor ($AUC(0-\infty)$) increased by 60% while C_{max} decreased by 21% compared to given alone. Therefore, exposure to GSK2881078 is expected to be within the safety margin at the proposed dose of 1 mg in women and 2 mg in men if a CYP3A4 inhibitor is co-administered with GSK2881078.”
	Information updated based on recent results from drug interaction studies that revealed much less interaction between CYP3A4 inhibitors and GSK 2881078 in healthy volunteers than previously expected from in-vitro data. Therefore, there is no reason to prohibit CYP3A4 inhibitors.
Section 6.2 Exclusion Criteria	Removal of reference to administration of strong oral or injectable cytochrome P-450 isoenzyme 3A4 (CYP3A4) inhibitors, and removal of criteria pertaining to consumption of fruit juices that are known CYP3A4 inducers (exclusion criteria 8 and previously numbered 19)	
Section 6.3.1 Meal and dietary restrictions	Removal of text that stated prohibition of “strong inhibitors” of CYP3A4, as well as removal of dietary requirements relating to these.	
Section 7.7	Removal of text referring to	

Section # and Name	Description of Change	Brief Rationale
Concomitant therapy	strong inhibitors of CYP3A4 Reiteration of prohibited medications that are listed in exclusion criterion 9 (drugs known to affect muscle mass)	
Section 6.2 Exclusion Criteria	Clarification of exclusion criteria to specify “pulmonary rehabilitation exercise program outside of inside the home”	Clarification of language to convey intent that a person participating in a formal pulmonary rehabilitation program, even if at home, would not be eligible for the study.
Section 9.2.1	Removal of reference to spirometry being measured at follow-up visit	Error in original protocol; revised wording is now consistent with the SoA.
Section 9.4 Treatment of overdose	Modification of definition of treatment overdose to any dose “above 1.0mg for females and 2.0mg for males within a 24-hour period”	Error in earlier protocol, which stated that any dose above 1.0mg would be considered an overdose.
Section 9.5.4 Clinical Laboratory Safety Assessments	Clarification that local laboratory tests conducted outside of the protocol that are clinically significant should be recorded in the “relevant section of the CRF, e.g. the SAE form.”	Clarification that there is not a separate CRF page for locally recorded results, but that these should be captured within the relevant CRF form.
Section 9.5.5 MRI scans	Addition of wording: In participants who agree to the MRI scans, every effort should be made to conduct all applicable MRI scans (cardiac and liver MRI for female participants, and additionally a prostate MRI for male participants). In circumstances where it is not feasible to continue performing all the MRI scans (e.g. patient discomfort), the cardiac scan should be prioritized over the liver or prostate scans.	Clarify that cardiac MRI scans should be prioritized in case consenting study participants and/or site staff deem it unfeasible to continue to perform all relevant MRI scans in the sub-study

Amendment 2: 22-AUG-2017

Overall Rationale for the Amendment: This amendment removes the stair climb test as a secondary endpoint in the study, as this test could not be standardized across multiple sites. The requirements for vitamin D deficiency as an exclusion criteria have been removed in response to study feasibility assessments. In addition, reference to an IDMC on page 69, which was included in error.

Section # and Name	Description of Change	Brief Rationale
Section 1 Synopsis Section 4 Objectives and Endpoints	Removal of stair climb from endpoints table	Stair climb test could not be standardized for 10 steps across multiple sites
Section 2 Schedule of Activities	Stair climb test removed from table for schedule of activities	
Section 5.4 Scientific rationale for study design	Text modified to read: Incremental and endurance shuttle walk test, with reference to stair climb deleted	
Section 9.2.3.3	Stair climb section deleted	
Section 10 Section 10.1.1. Section 10.1.3 Section 10.3.3	“Stair climb power” deleted throughout main text and table column titled “Stair climb power”	
Section 1 Synopsis Section 4 Objectives and Endpoints	Removal of the “adherence to exercise program” secondary endpoint from the table in sections 1 and 4, and addition of following wording in exploratory endpoints in section 4: “Potentially explore adherence to	Whilst adherence to the home exercise program remains of interest, the home exercise program is being piloted in this study, therefore the dataset can only be explored if it is sufficiently complete.

Section # and Name	Description of Change	Brief Rationale
	exercise program (daily physical activity and thrice-weekly strengthening exercises)"	
Section 2 Schedule of Activities	Visits numbered (V1, V2, V3, V4, V5, V6, V7, V8 and V9)	Visit labels added to help ease of reference for participants and site staff
Section 2 Schedule of Activities	'x' removed from cell for Day 90 visit in the row 'Study treatment provided'	Error in original protocol; treatment is not provided at the end of treatment visit
Section 2 Schedule of Activities	Reference to whole body MRI removed and replaced with 'Cardiac and liver MRI (additionally prostate MRI in males)'	The whole body MRI is looking specifically at the heart, liver and, in males, the prostate therefore the wording was amended throughout the protocol for clarity.
Section 3.3.1	Whole body MRI replaced with cardiac MRI	
Section 4 Objectives and Endpoints	"Whole body" deleted from description of MRI	
Section 9.1.3 Baseline (day 1) and last dose (day 90) visits	Text modified to read "At some study sites, optional cardiac, liver and prostate MRI scans will be offered to eligible participants."	
Section 9.5.5 Whole Body MRI scan	"Whole body" deleted from section heading Reference to "whole body" in main text replaced with "cardiac, liver and prostate"	
Section 2 Schedule of Activities	Footnote number 2 amended: As stated in Section 8.2, if a participant decides to withdraw or is withdrawn by the responsible physician, the reasons for withdrawal and the results of any relevant tests will be recorded in	This was reworded to help clarify that only the safety assessments at the follow-up visit would be conducted in case of withdrawal from the study.

Section # and Name	Description of Change	Brief Rationale
	
the CRF and the planned safety follow-up procedures will be performed, where possible. These include physical examination, 12-lead ECG, vitals, blood tests, urinalysis and concomitant medication review as listed for the follow-up visit (V9).
 
The following text was deleted:
 
The leg press should be prioritized over other functional assessments.
 
Safety assessments to be collected at follow-up visits in case of study discontinuation or withdrawal of participants are as follows: physical examination, 12-lead ECG, vitals, blood tests, urinalysis and concomitant medication review as listed for the follow-up visit
	
Section 5.1 Overall Design	
Text modified with following additions:
 
“Site staff will supervise performance of the initial exercises to assess which of the four exercises can be prescribed to participants, as well as setting the baseline intensity for the exercises and clarifying instructions from the home exercise Application.”
 
“Guidance for performing exercises and setting goals will be given by the home exercise Application from the baseline visit onwards, however participants will have the opportunity to raise any concerns they have with site staff.”
	
Additional text with clarification on supervision of the home exercise program was added in response to comments from ethics committees.

Section 6.2 Exclusion	
The following text was deleted:
 
Deficient levels (<20 ng/mL) of 25-
	
Vitamin D deficiency is likely present in a significant portion of our target study population, and likely to pose a significant

Section # and Name	Description of Change	Brief Rationale
Criteria Page 31	OH Vitamin D Total; NOTE: Participants with insufficient (20 – 29 ng/mL) levels may be enrolled.	barrier to recruitment. Since it should not interfere with the study drug mechanism, therefore the decision was made to remove.
Section 8.2	Text added “or an exacerbation that requires treatment with oral steroids”	To clarify that any steroid use requires participants to withdraw from the study
Section 12.2 Appendix 2	“days” added after 125	Clarify duration of contraception use – error in original protocol
Section 12.3 Appendix 3	Reference to IDMC removed	Originally included in error, as there is no plan to have an IDMC for this study

Amendment 1: 19-MAY-2017

Overall Rationale for the Amendment: This amendment removes reference to measurement of lumbar bone density, as this requires an additional Dual-Energy X-ray Absorptiometry (DXA) scan to the ones for measurement of muscle mass, thus reducing radiation exposure for subjects.

Section # and Name	Description of Change	Brief Rationale
Section 3.3.1 Risk assessment	Remove reference to measurement of lumbar bone density in the risk mitigation strategy for bone effects	Not required as no longer performing DXA scans for measurement of bone density.

1. SYNOPSIS

A randomized, double-blind (sponsor unblind), placebo-controlled, multi-centred phase IIa study to evaluate the safety and efficacy of 13 weeks of once daily oral dosing of the selective androgen receptor modulator (SARM) GSK2881078 in older men and post menopausal women with COPD and muscle weakness, participating in home exercise

Short Title: A randomized, double-blind, placebo-controlled study to evaluate the safety and efficacy of 13 weeks of the selective androgen receptor modulator (SARM) GSK2881078 in COPD

Rationale:

This study is the third clinical study with administration of GSK2881078 in humans, and it will be the first administration to the target population, defined as older men and post-menopausal female participants (50-75 years of age) with chronic obstructive pulmonary disease (COPD) and muscle weakness, participating in home exercise. This study will evaluate the safety and tolerability over 13 weeks of dosing in this population. This study will also evaluate the anabolic effects of GSK2881078 as measured by changes from baseline in leg strength, muscle mass, and functional measures.

Objectives and Endpoints:

Objectives	Endpoints
Primary	

 Assess the safety and tolerability of approximately 13 weeks of dosing of GSK2881078 	
 Safety and tolerability of GSK2881078 as assessed by clinical monitoring of blood pressure, heart rate, electrocardiogram (ECG) and laboratory safety data, as well as reporting of adverse events (AEs)

 Assess the effect of approximately 13 weeks of dosing of GSK2881078 on leg strength in older men and post-menopausal women with COPD and muscle weakness, participating in home exercise 	
 % change from baseline and change from baseline in maximum leg press strength following 1 repetition maximum (1- RM)
Secondary	

 Assess the effect of approximately 13 weeks of dosing of GSK2881078 on lean soft tissue mass 	
 Change from baseline in appendicular, and total lean mass as assessed by Dual-energy X-ray Absorptiometry (DXA)

Objectives	Endpoints

 Assess the effect of approximately 13 weeks of dosing of GSK2881078 on exercise capacity 	
 Change from baseline in total Short Physical Performance Battery (SPPB) score and times for chair rise and 4 m gait speed Change from baseline in Constant Work Rate (CWR) duration from endurance shuttle walking test Change from baseline in peak performance from incremental shuttle walking test

 Assess the effect of approximately 13 weeks of dosing of GSK2881078 on patient reported outcomes, levels of physical activity, activities of daily living and the patient perspective of efficacy 	
 Change from baseline in COPD Assessment Test (CAT) Change in PROactive endpoints (individual components and total score) Change in physical activity measures as assessed via an accelerometer Patient Global Impression of Change Patient Global Rating of Severity Change in St George Respiratory Questionnaire-COPD (SGRQ-c) total score and domains

 Assess the effect of approximately 13 weeks of dosing of GSK2881078 on respiratory function 	
 Change from baseline in forced expiratory volume in 1 second (FEV1) Change from baseline in Sniff nasal inspiratory pressure (SnIP)

 Characterise the population pharmacokinetic (PK) profile of approximately 13 weeks of dosing of GSK2881078 in older men and post-menopausal women with COPD and muscle weakness 	
 Model specific PK parameters of GSK2881078 (e.g., oral clearance, oral steady-state volume of distribution).

Additional exploratory analyses related to the primary and secondary endpoints will also be performed.

Overall Design:

This study is a randomized, placebo-controlled, double-blind (sponsor unblind), parallel group trial in two equal sized cohorts (male or female) of participants with COPD.

Following completion of screen assessments, baseline assessments will be conducted in eligible participants and, in each cohort, the participants will be randomized 1:1 to GSK2881078 or matching placebo.

Number of Participants:

At least 100 participants with COPD and muscle weakness will be randomized (25/arm) to target approximately 80 evaluable participants (20/arm). Men and women will be recruited into separate cohorts of at least 50 participants each, with each cohort containing 1:1 allocation of placebo and GSK2881078.

Additional participants may be enrolled if the number of participants with exacerbations plus the number of participants withdrawn prematurely for other reasons is higher than anticipated (approximately 20%), based on differences in observed variability in endpoint parameters and the ability to detect a treatment effect at interim. The total sample size may be increased by up to 60 participants (approximately 15/arm). Enrolment is not expected to exceed approximately 160 total participants.

Treatment Groups and Duration:

The study will consist of a screening/baseline period of up to 30 days, a 13-week treatment period, and a 6 week (42 days) post-treatment follow-up visit. Study participation, including screening and follow-up, is not expected to exceed 6 months for participants in the study.

Study treatment will consist of two dosing cohorts (Male: placebo or 2.0 mg once daily of GSK2881078; Postmenopausal female: placebo or 1.0 mg once daily of GSK2881078). All participants will take their first dose of study treatment in the clinic following randomization. Participants will be dosed without regards to food intake.

2. SCHEDULE OF ACTIVITIES (SOA)

Procedure	Screening V1 (up to 30 days before Day 1)	V2 Day -9	Treatment Period (13 weeks)							Follow- up ² V9 (42 days post last dose)	Notes
			V3 Baseline Day 1	V4 Day 14	V5 Day 28	V6 Day 56	V7 Day 80	V8 Last dose 90	Unscheduled visit ¹		
Visit window (days)	- 30 to -11	-11 to -7	-2 to day 1	12 - 16	24 - 32	52- 60	76 - 84	85 - 91		126- 140	There should be an attempt to conduct all assessments for a visit within a single day ³ .
Informed consent	X										Obtained prior to performing any study-related procedures.
Inclusion and exclusion criteria	X										
Demography/ medical/medication/ drug/ alcohol history/ PD disease staging	X										
Full physical examination	X									X	X
Brief physical exam			X	X	X	X		X			
12-lead ECG	X		X	X	X	X		X	X	X	
Vital signs	X		X	X	X	X		X	X	X	
HIV, Hepatitis B and C screening	X										If test otherwise performed within 3 months prior to first dose of study treatment, testing at screening is not required
Hepatitis C viral RNA PCR									X		If evidence of Hepatitis C antibodies at screening visit, then Hepatitis C viral RNA PCR required to exclude active infection. This sample is not needed if Hepatitis C screening is negative.

Procedure	Screening V1 (up to 30 days before Day 1)	V2 Day -9	Treatment Period (13 weeks)							Follow- up ² V9 (42 days post last dose)	Notes
			V3 Baseline Day 1	V4 Day 14	V5 Day 28	V6 Day 56	V7 Day 80	V8 Last dose 90	Unscheduled visit ¹		
Haematology (Full blood count)/ Clinical Chemistry (Creatinine, urea and electrolytes, liver function tests, glucose)	X		X	X	X	X		X	X	X	Participants should fast overnight for at least 8 hours prior to collection of these samples.
HbA1c	X							X			
hsCRP, Fibrinogen			X					X		X	
25-OH Vitamin D Total, 25-OH Vitamin D2, 25-OH Vitamin D3	X							X		X	
Lipid panel	X		X	X	X	X		X		X	
Genetic sample			X								Obtain after participant is randomized. Informed consent to obtain the genetics sample must be obtained before collecting a sample.
Pharmacokinetic sampling				X ⁴	X ^{4,5}	X ⁶		X ⁴	X		Times of dose administration for the two doses immediately preceding a PK sample should be accurately recorded.
Reproductive Tissue Biomarkers			X		X	X		X		X	
PSA	X		X		X	X		X		X	For male participants only
Bone Biomarkers			X		X			X		X	
Exploratory Biomarkers			X	X	X			X		X	
Urinalysis	X		X					X	X	X	
DXA			X		X	X		X	X	X	
Spirometry	X		X			X		X			Follow ATS/ ERS guidelines [Celli, 2004] and Quanjer reference equation [Quanjer, 2012].

Procedure	Screening V1 (up to 30 days before Day 1)	V2 Day -9	Treatment Period (13 weeks)							Follow- up ² V9 (42 days post last dose)	Notes
			V3 Baseline Day 1	V4 Day 14	V5 Day 28	V6 Day 56	V7 Day 80	V8 Last dose 90	Unscheduled visit ¹		
Sniff Nasal Inspiratory Pressure	X		X			X		X			
Leg strength	X		X		X	X		X		X	
Handgrip strength	X		X					X			
Short Physical Performance Battery	X		X		X	X		X		X	
Incremental Shuttle Walk Test		X	X					X			Practice incremental shuttle walk test conducted at day -9
Endurance Shuttle Walk Test			X					X			
COPD Assessment Test			X			X		X			
St George Respiratory Questionnaire COPD (SGRQ-c)			X					X			
Patient Global Rating of Severity			X					X			
Patient Global Impression of Change				X	X	X		X		X	
Daily PROactive Physical Activity in COPD instrument and Physical Activity Monitor	X	X ⁷				X	X ⁷				Physical activity monitor dispensed at screening, day -9, day 56 and day 80 visits. Activity monitor should be worn for 7 days at each timepoint and returned at the next visit.
Monitored home exercise program		X	X	<=====>				X			Participants will receive training for the exercise program at Day -9, and will formally begin exercises on day 1
Patient exit interview										X	
Randomization			X								All Baseline assessments must be obtained prior to randomization.
Study treatment provided to participant			X		X	X					The subject should take their first dose of study treatment in the clinic after randomization.

Procedure	Screening V1 (up to 30 days before Day 1)	V2 Day -9	Treatment Period (13 weeks)							Follow- up ² V9 (42 days post last dose)	Notes
			V3 Baseline Day 1	V4 Day 14	V5 Day 28	V6 Day 56	V7 Day 80	V8 Last dose 90	Unscheduled visit ¹		
Study treatment			X	←=====→				X			Participants should dose study treatment in the clinic at each clinic visit during the treatment period.
Study treatment accountability by study site			X	X	X	X		X			The required counting of pills by site staff to check compliance is not considered redispensing the study medication.
AE review			X	←=====→					X		
SAE review			X	←=====→					X		
Concomitant medication review			X	←=====→					X		
Optional sub-study measures											
Cardiac and liver MRI (additionally prostate MRI in males)			X ⁸					X ⁸			MRI is an optional assessment undertaken at participating centres only.

ECG= Electrocardiogram; HIV= Human Immunodeficiency Virus; PK= Pharmacokinetic; PSA= Prostate Specific Antigen; DXA= Dual-energy X-ray Absorptiometry; AE= Adverse Event; SAE= Serious Adverse Event.

1. An unscheduled clinic visit may occur at any time if the investigator believes an unscheduled visit is clinically warranted. Individual listed assessments are optional and are performed as needed to follow unresolved findings of clinical concern. Note: The “Unscheduled visit” case report form (CRF) form should be completed as soon as possible following the Unscheduled visit.
2. As stated in Section 8.2, if a participant decides to withdraw or is withdrawn by the responsible physician, the reasons for withdrawal and the results of any relevant tests will be recorded in the CRF and the planned safety follow-up procedures will be performed, where possible. These include physical examination, 12-lead ECG, vitals, blood tests, urinalysis and concomitant medication review as listed for the follow-up visit (V9).
3. Attempt to conduct all visits within a single day however the baseline (day 1) and last dose (day 90) visits may require subjects to visit the study centre on more than one day in order to complete MRI and DXA scans, and possibly other assessments. These

scans, and any other assessments, should be conducted within the specified visit window, and prior to randomization at the baseline visit. Further details on the suggested order of assessments will be given in the SRM.

4. Take PK sample prior to dosing in the clinic
5. Take PK sample 1-4 hours post-dose (sites should try and ensure that a range of times are sampled within this time window for different participants, i.e. all PK samples should not be taken at 1 hour post dose or 2 hours post dose).
6. Take PK sample 5-8 hours post-dose (as above, sites should try and ensure that a range of times are sampled within this time window for different participants).
7. At V3 Baseline Day 1 and V8 Last dose 90, the patients will return the Daily PROactive Physical Activity in COPD Instrument and the Physical Activity Monitor to the site. Patients will not be dispensed the Daily PROactive Physical Activity in COPD Instrument and the Physical Activity Monitor at the end of these visits.
8. All MRI Scans (Cardiac MRI, Liver MRI and, if applicable, Prostate MRI) should preferably be scheduled on the same day. Acquisition of the Cardiac MRI should be prioritized above the other two scans if it becomes unfeasible to perform all the MRI scans.

The following points must be noted:

- If assessments are scheduled for the same nominal time, THEN the assessments should occur in the following order:
 - i. vital signs
 - ii. 12-lead ECG
 - iii. blood draws.

Note: The timing of the assessments should allow the blood draw to occur at the time specified in the SoA

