A physical activity monitor will be worn for 7 days at screening for eligible participants, 7 days after the Day -9 visit, for 7 days after the Day 56 visit, and for 7 days following the day 80 visit. During those periods, participants will rate their physical activity on a daily basis by completing the PROactive eDiary. In addition, participants will be asked to complete additional questionnaires CAT which assesses the impact of COPD on a patient's life, Patient Global Rating of Severity (PGRS), Patient Global Impression of Change (PGIC) during scheduled clinic visits as specified in the SoA Time and Events table (Section 2).

Participants will return to the clinic for a follow-up visit 42 days (± 7 days) after the final dose of study treatment to undergo safety evaluations and final functional assessments. In addition, all remaining study medication that was not returned at the last treatment visit (i.e., Day 90) will be returned to the clinical unit for final drug accountability.

The study duration, including screening and follow-up, is not expected to exceed 6 months for participants in the study.

Unblinded data will be reviewed in-stream by the GSK clinical study team and the safety review team (SRT). If, at any time, the 2.0 mg dose in men or the 1.0 mg dose in women, has a safety signal of clinical concern, treatment will be stopped.

An interim analysis for the assessment of futility is planned. It is anticipated that a formal declaration of futility would not be made before at least 10 participants per group have completed dosing and all key study assessments. However, if at any time it is determined that the probability of a successful outcome is sufficiently low, recruitment could be stopped. The primary endpoint for assessment of futility is strength. However, the decision to continue or stop recruitment will be made by the unblinded GSK clinical study team and Safety Review Team (SRT) based on the evaluation of all available safety, efficacy, and tolerability data. Such decisions will be based on the totality of the data (including strength, lean mass, function, safety, and tolerability). See Section 10 for more detail. The feasibility of making a decision to stop recruitment based on a futility analysis will be dependent on the recruitment rate. Futility will be evaluated separately for female and male participants.

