8. DISCONTINUATION CRITERIA

8.1. Discontinuation of Study Treatment

A participant may discontinue treatment if they have a severe exacerbation of COPD requiring hospitalization or if they meet liver or QTc stopping criteria. A participant who discontinues study treatment should return to the clinic only for the follow-up visit within the specified window if possible. Only the safety assessments for the follow-up visit (physical examination, 12-lead ECG, vitals, blood tests, urinalysis and concomitant medication review) should be conducted in these participants as described in the SoA and Section 9.4.

[figure not shown]

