8.2. Withdrawal from the Study

- A participant may withdraw from the study at any time at his/her own request, or may be withdrawn at any time at the discretion of the investigator for safety, behavioral, compliance or administrative reasons.
- If the participant withdraws consent for disclosure of future information, the sponsor may retain and continue to use any data collected before such a withdrawal of consent.
- If a participant decides to withdraw or is withdrawn by the responsible physician, the reasons for withdrawal and the results of any relevant tests will be recorded in the CRF and the planned follow-up procedures will be performed, where possible.
- If a participant withdraws from the study, he/she may request destruction of any samples taken and not tested, and the investigator must document this in the site study records.
- Refer to the SoA for data to be collected at the time of study discontinuation and follow-up and for any further evaluations that need to be completed. Only the safety assessments scheduled for the follow-up visit should be conducted in these participants as described in the SoA (Section 2).
- **Any participant who experiences a severe COPD exacerbation (i.e., associated with hospitalization or emergency room visit) or an exacerbation that requires treatment with oral steroids will be permanently discontinued from study treatment and should return to the clinic for the follow-up visit within the specified window if possible. Only the safety assessments scheduled for the follow-up visit should be conducted in these participants as described in the SoA (Section 2).**

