## 12.3. Appendix 3: Assessment Windows

### 12.3.1. Definitions of Assessment Windows for Analyses

Analysis Set / Domain	Parameter (if applicable)	Protocol Window		Target	Analysis Window		Analysis Timepoint
		Beginning Timepoint	Ending Timepoint		Beginning Timepoint	Ending Timepoint	
All	All	Day -30	Day -11	Day -30 to -11	Day -60	Day -12	Screening/Visit 1
All	All	Day -11	Day -7	Day -9	Day -11	Day -5	Visit 2
All	All	Day -2	Day 1	Day 1	Day -4	Day 1	Visit 3, Day 1
All	All	Day 12	Day 16	Day 14	Day 10	Day 18	Visit 4, Day 14
All	All	Day 24	Day 32	Day 28	Day 22	Day 34	Visit 5, Day 28
All	All	Day 52	Day 60	Day 56	Day 50	Day 62	Visit 6, Day 56
All	All	Day 76	Day 84	Day 80	Day 76	Day 84	Visit 7, Day 80
All	All	Day 85	Day 91	Day 90	Day 85	Day 97	Visit 8, Day 90
All	All	Day 126	Day 140	Day 132	Day 126	Day 140	Follow-Up, Day 132

- For scheduled visits the analysis visit would equal the nominal visit irrespective of the assessment date and irrespective of whether that date falls in the visit window.
- Only unscheduled visits are slotted according to the table above and this slotting algorithm will be applicable for both efficacy and safety domains.
- After slotting of Un-scheduled visits, if there are multiple assessments at a planned timepoint, then the value closest to the target day for that window will be considered. If the multiple assessments are equidistant from the target day, then mean of the assessments will be considered.
- For any time post baseline and baseline (if the definition of baseline is the latest pre-dose visit) all assessments are used irrespective of whether they fall into visit windows or not.

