## 12.7. Appendix 7: Reporting Standards for Missing Data

### 12.7.1. Premature Withdrawals

Element	Reporting Detail
General	
 
• Subject study completion (i.e. as specified in the protocol) was defined as subjects who completed all visits of the study including the follow-up visit.
 
• Withdrawn subjects may be replaced in the study.
 
• All available data from participants who were withdrawn from the study will be listed and all available planned data will be included in summary tables and figures, unless otherwise specified.
 
• Withdrawal visits will be assigned to a planned visit or an unscheduled visit and will be slotted as per Appendix 3: Assessment Windows.
 

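### The timing of the follow-up visit is undetermined for participants who stop early, and the SAP leaves a route by which their off-drug safety values could be summarised as Day 56 or Day 90

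*Protocol*

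**What the plan says.** The protocol gives the follow-up visit two anchors. The Schedule of Activities (Section 2) heads the column "V9 (42 days post last dose", and Section 5.1 adds a tolerance: "Participants will return to the clinic for a follow-up visit 42 days (± 7 days) after the final dose of study treatment". The window row of the same schedule, however, gives fixed study days, 126 to 140.

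Early stoppers are sent to this visit. Section 8.1 says: "A participant who discontinues study treatment should return to the clinic only for the follow-up visit within the specified window if possible". Section 8.2 repeats the instruction after a severe or steroid-treated exacerbation: "should return to the clinic for the follow-up visit within the specified window if possible". Neither section says which window is meant. Only safety assessments are done at that visit, and Section 8.1.3 makes stopping treatment a withdrawal from the study.

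The SAP carries only the fixed window (12.3.1, analysis timepoint "Follow-Up, Day 132", Days 126–140). Three SAP statements then bear on how an early stopper's visit is classified:

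- The notes under the table in 12.3.1 keep scheduled visits at their nominal label whatever the date, and slot only unscheduled visits by study day.
- Section 12.7.1 says: "Withdrawal visits will be assigned to a planned visit or an unscheduled visit and will be slotted as per" Appendix 3.
- The footnote to mock listing POP_L2 (Appendix 12) derives the analysis visit by running the slotting algorithm on the visit start date, with no exception for scheduled visits.

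Section 12.5.2 allows slotted unscheduled visits into by-visit summaries. Section 12.4.1 splits only concomitant medication by treatment phase.

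**The concern.** Safety is a primary endpoint, and participants who stop early include those who met liver or QTc stopping criteria. For them V9 is the only planned visit left. If its date is ambiguous, sites may examine similar participants at very different intervals after the last dose. Adverse events are collected up to this visit (protocol 9.3.1), so the length of event capture varies with it.

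The analysis question follows from the pharmacology. Protocol 3.3.1 reports an HDL fall of roughly 30–40% at maximal effect, returning to baseline after dosing ended. Section 5.5 says the HDL, testosterone and SHBG changes were reversible on stopping. A recovered value labelled Day 56 or Day 90 would make the active arm's on-treatment change look smaller than it was.

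**Working it through.** **Inputs.** Relative rule: 42 ± 7 days after last dose (protocol 5.1). Fixed window: Days 126–140 (Schedule of Activities; SAP 12.3.1, target Day 132). Last-dose visit: Days 85–91. SAP analysis windows: Day 14 = 10–18, Day 28 = 22–34, Day 56 = 50–62, Day 80 = 76–84, Day 90 = 85–97. Half-life: 5–8 days (protocol 5.5). Let L be the study day of the last dose.

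**1. Reproduce the plan's window.** The relative window is L + 35 to L + 49.
- L = 91: Days 126–140, exactly the fixed window.
- L = 90: target 90 + 42 = 132, the SAP target; window Days 125–139.
- L = 85: target 127; window Days 120–134, overlapping the fixed window on Days 126–134.

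**2. Where the rules can both be met.**
- Any common date requires L + 49 ≥ 126, so L ≥ 77.
- The 42-day target lies in the fixed window if L + 42 ≥ 126, so L ≥ 84. This covers all completers (L = 85–91).
- For L < 77 no date satisfies both.

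**3. Example, L = 30.** Relative rule: 30 + 35 = 65 to 30 + 49 = 79, so Days 65–79. Fixed window: 126 − 30 = 96 to 140 − 30 = 110, so 96–110 days off drug.

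**4. Slotting, if the visit is handled as a withdrawal or unscheduled visit.** Put V9 at exactly L + 42 for L = 1 to 83, the stop days whose 42-day target misses the fixed window.

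| Last dose (L) | Visit day (L + 42) | SAP slot | Stop days |
|---|---|---|---|
| 8–20 | 50–62 | Day 56 | 13 |
| 34–42 | 76–84 | Day 80 (no planned labs) | 9 |
| 43–55 | 85–97 | Day 90 | 13 |
| 1–7, 21–33, 56–83 | other | none | 48 |

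Total: 13 + 9 + 13 + 48 = 83. Stop days leading to a planned on-treatment laboratory visit: 13 + 13 = 26, and 26/83 = 31%. Allowing the ± 7 days, the Day 56 slot can be reached from last doses on Days 1–27 and the Day 90 slot from Days 36–62.

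**5. Are these off-drug values?** Assuming simple first-order decay, the fraction of drug left at 42 days is 2^(−42/5) = 0.3% to 2^(−42/8) = 2.6%. They are.

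**6. Illustration of dilution.** Take 20 on-drug values in an arm (the evaluable target) and add k slotted values assumed fully recovered. The mean change is multiplied by 20/(20 + k). A 30% HDL fall would read 30 × 20/21 = 28.6% for k = 1 and 30 × 20/22 = 27.3% for k = 2. The documents give no basis for predicting k.

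**The case against.** The strongest reply is the nominal-visit rule in SAP 12.3.1. V9 is a scheduled, labelled visit, and an early stopper's visit recorded as V9 stays in Follow-Up on any study day. Section 12.7.1 can be read consistently with this: a withdrawal visit assigned to a planned visit is handled under Appendix 3, which contains that rule. This stands. A reader might infer from the window table that an early stopper's V9 can never reach Follow-Up, and the SAP does not support that. What remains is that 12.7.1 also provides for an unscheduled assignment and says withdrawal visits are slotted, and that the POP_L2 footnote applies the algorithm without exception. The SAP does not say which governs.

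It can also be said that Days 126–140 is simply Day 91 + 42 ± 7, the completer's version of the same rule. That is right, so the two anchors should not be called incompatible for everyone. Nor is the early stopper's visit shown to be mistimed: a site following Section 5.1 times it as that section states. The fault is that Sections 8.1 and 8.2 do not say which window applies.

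Finally, other safeguards exist. Unscheduled visits are possible at any time, liver stoppers have their own monitoring (Appendix 4), all unscheduled visits are listed, and any-time post-baseline summaries already pool on- and post-treatment data. These limit the harm, but they do not correct a by-visit mean.

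**Conclusion.** The point holds in two parts. First, for a last dose before Day 77 the protocol's two statements of the V9 window cannot both be met, so the timing of the one planned safety visit is undetermined. Completers are essentially unaffected. Second, the SAP's classification rules conflict, and one permitted route puts off-drug values into the Day 56 or Day 90 safety summaries, with no on/off-treatment filter to remove them. Values falling in no slot would drop out of the by-visit summaries.

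The slotting result rests on two assumptions: the visit is treated as a withdrawal or unscheduled visit, and it takes place 42 days after the last dose. The 26 of 83 counts calendar days with equal weight. A reader might take 31% as a share of participants, or multiply it by the roughly 20% combined exacerbation and withdrawal rate in protocol 5.2. Neither is supported, because the documents give no distribution of stopping times and that rate covers both arms.

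A reader might also infer bias in the primary strength analysis. Early stoppers have only safety assessments at V9, so the planned leg-press data in the repeated-measures model are not affected. The effect is confined to descriptive by-visit lipid, hormone, other laboratory, ECG and vital-sign summaries. In arms of about 20–25 a few misplaced values would be noticeable but not dominant.

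**What to change.** **Protocol.** Reconcile the Schedule of Activities header and window row with Sections 5.1, 8.1 and 8.2, so that one stated window covers completers and early stoppers and the two discontinuation sections point to it. Which window applies is the sponsor's decision.

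**SAP.** Reconcile 12.3.1, 12.7.1 and the POP_L2 footnote:

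- V9 is always analysed as Follow-Up by its label, with days since last dose reported.
- Withdrawal or unscheduled data collected at a post-treatment visit after the last dose are not slotted to Day 14 through Day 90 in by-visit safety summaries. They remain in listings and any-time post-baseline summaries.

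**Cost.** Clarifying wording in the protocol sections named, a few SAP sentences, and a small programming check on last-dose date. No extra visits, assessments or data are needed.
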